Treatment of post-UFE pain and PES has largely focused on the use of non-steroidal anti-inflammatory medications (NSAIDs), narcotics, antiemetics, intra-arterially delivered lidocaine, and most recently with dexamethasone. It is this last option that has shown a decrease in both pain scores and biomarkers of inflammation [21]. In this study by Kim, et. al., significant reductions in post-procedural pain were achieved with a single intravenous dose of 10mg of dexamethasone without any reported complications [3]. Our hypothesis is primarily based on this Randomized study. Instead of giving the steroid orally, administration into uterine artery will lead to a high dose of drug reaching the myometrium, bypassing the first pass metabolism and systemic drug dilution. We hypothesize that the anti-inflammatory effects of the high dose dexamethasone will have a significant beneficial effect on the post procedural pain and PES.

As a single administration, even at high doses, dexamethasone has very favorable efficacy and side effect profiles for the treatment of a wide range of conditions, including inflammation, pain, and nausea [22]. In fact, a recent study involving a single IV dose of dexamethasone was shown to significantly decrease PES following embolization of liver tumors [23].

Delivering dexamethasone directly to the uterus during a UFE has several advantages: bypassing of the first-pass metabolism, the lack of systemic dilution, and importantly, the direct delivery to the targeted region of ischemia and source of pain- *i.e.* the same tissue receiving embolic agent will also receive dexamethasone. This will also be administered as a single dose, eliminating the need for a steroid taper. This is a relatively cheap intervention (cost of Dexamethasone \$1.22 USD per dose) which could potentially save money by decreasing the length of hospital stay and transitioning of UFE to an ambulatory/outpatient procedure. Additionally, a concurrent decrease in the incidence of PES should translate to a lower readmission

rate. If true, this work may also have a social impact in that fewer narcotics would be required to control pain. Here we propose a clinical trial designed to address these questions, and if proven true, could be adopted as a standard of practice to this uterine-sparing minimally-invasive procedure.

8. Inclusion and Exclusion Criteria*

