- Current medication requirements (e.g. OCPs, NSAIDs, narcotics, anti-emetics) will also be assessed at this time.
- Basic laboratory studies will be conducted at this time. This will include a Complete Metabolic Panel (CMP), Complete Blood Counts (CBC), Hemoglobin A1c, and qualitative urine pregnancy test (UPT).
- Each patient will further undergo (or have recent) pre-procedural imaging to determine fibroid burden, approximate volume, and arterial anatomy. This should be an MRI of the pelvis.

Uterine Embolization Procedure:

No changes are proposed to the standard UFE procedure except for the intraarterial delivery of dexamethasone.

Pre-UFE patients will receive the following medications for conscious sedation, pain control and nausea/vomiting during the procedure as per the standard departmental protocol, unless contraindicated:

- 50-300 mg IV Fentanyl
- 0.5- 3.0 mg IV Versed
- 30 mg IV Toradol
- 1 g IV acetaminophen

Procedure technique:

No changes are proposed to the standard UFE procedure except for the intraarterial delivery of dexamethasone.

Common femoral or radial artery access is used for the procedure. Using a combination of base catheters, microcatheters and different wires, each uterine artery is catheterized and angiograms are performed. *Following this, prior to embolization, 5 mg of IV dexamethasone or placebo are injected via the microcatheter placed in the uterine artery.* This is followed by particle embolization using particles of size ranging from 500-1000 μ M, until near stasis as per standard technique. The same procedure is then repeated on the contralateral uterine artery. Finally, catheters and sheaths will be removed and hemostasis achieved at the access sites using closure device or manual compression. Patients will be admitted to the general medicine ward for overnight observation.

Post-UFE patients will receive the following pain/anti-emetic regimen post procedure:

Inpatient Medications

- 30 mg IV Ketorolac q6h
- 650 mg PO Acetaminophen q6h (continued for 4 days post procedure)
- 0.2 mg demand dose, 10 minute lockout, 1.2 mg/hour, Hydromorphone PCA
- 4 mg IV Ondansetron q6h PRN

Discharge Medications

- 650 mg PO Acetaminophen q6h (4 days post procedure, then q12h)
- 800 mg PO Ibuprofen q6h (4 days post procedure, then q12h)
- 5/325 mg PO Percocet q6h PRN
- 100 mg PO Docusate Sodium (Colace) q12h (4 days post procedure, then PRN)
- 4 mg SL Ondansetron q6h PRN

Post-Procedure Assessment and Imaging:

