- *Pain, nausea, vomiting and fever will be documented using the visual analog score and nausea and vomiting score at:*
 - *Time 0 Immediately prior to the procedure*
 - *1 hour intervals for the first 3 hours*
 - *3 hour intervals for the next 9 hours*
 - *6 hour intervals for the next 12 hours*
 - *Daily, for the next 3 days*
 - *Once at day 7*
- *Each patient will complete uterine fibroid symptom & health-related quality of life questionnaire prior to the procedure and then 1 month and 3 month after.*
- Each patient will undergo post-procedural MRI imaging to determine residual fibroid burden and approximate volume at 3 months in order to gauge treatment response.
- PCA usage statistics.

Study Design:

This study is designed as a double blinded, placebo controlled randomized control trial. As previously mentioned, the study will divide the patients into two groups. The test group will receive intra-procedural intra-arterial dexamethasone and the control group, a saline placebo. Block randomization (Size: 8) will be done using a random number generator.

The drug or placebo will be prepared by research pharmacy and be delivered to the Interventional Radiology Department in identical containers with specific serial numbers. The physician performing the UFE, the patient and the research team will be unaware of the nature of the administered drug/placebo or the patient grouping. The drug preparation will be coordinated by the University of Miami Pharmacy Department's Research Coordinator, [name]. Once the uterine artery is catheterized, the drug or placebo will be injected intra-arterially. Embolization is then performed as usual.

Following UFE, all patients will be admitted to the general inpatient unit for observation, as is standard of care for all UFE patients. Following this observation period, patients will be discharged with appropriate instructions of when and how to follow-up with the treatment team. This will include explicit instructions to self-monitoring for unusual bleeding, swelling, bruising at the femoral artery access site, abnormal uterine bleeding, cramping, extended bouts of nausea, vomiting, fever, chills, and malaise. All patients will be given the number of an on-call physician for questions and concerns they may have. As mentioned above, all patients will be telephoned daily by a member of the research team on day 2, 3, 4, and 7 post-UFE.

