Participants will be introduced to the study at the time of their initial clinical visit, and a standardized questionnaire will be administered by the primary physician with standardized teach-back techniques to ensure patient understanding of the risks and benefits of the altered procedure [24]. Participants will not be obligated to enter into the study at this time, and can do so, at any time prior to the procedure.

The patient will be given the following documents, which are included in this proposal, during the initial visit:

IRB Study Number:

Version: 05282020

Date: 05/28/2020

1. Procedural Consent Form (IMed UFE Consent Form)
2. Study Informed Consent
3. Study Timeline Graphic
4. Adverse Event Reporting Form (FDA Form 3500)
5. UFE Pain & PES Survey
6. QOL Survey

Non-English Speaking Subjects

- Spanish
- Portuguese
- French
- French Creole (French and Haitian)
- Chinese (Mandarin and Cantonese)

All participants will be consented and instructed by a certified native linguist or translation phone line, used by the University of Miami Hospital System.

34. Process to Document Consent in Writing

We will utilize the consent form attached at the end of this document, Study Consent Form, a derivative of HRP-502a.

35. Authorization for Use and Disclosure of Protected Health Information (HIPAA)

Type of Request:

Waiver of Authorization for access to medical record for subject identification/recruitment.

Waiver of Authorization for access to medical record to obtain data for the research.

Confirm that you will destroy or de-identify the information you collect at the earliest opportunity.

I confirm

Confirm that the information you collect will not be reused or disclosed to any other person or entity, except as required by law, for authorized oversight of the research study or for other research for which the use or disclosure of PHI is permissible.

I confirm

36. Drugs or Devices

All vials/syringes of dexamethasone or saline will be compounded by the Pharmacology Research Coordinator, [name], BCOP, BCPS, at University of Miami Hospital. 8 mg dexamethasone intravenous preparation or placebo will be dispensed in identical vials or syringes with unique serial numbers. A log of the serial numbers will be kept in the pharmacy. The medication will be delivered to the IR Angiography suite and will be administered by the interventional radiologist performing the procedure. Storage is not required as the drug is prepared and administered the same day.

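### Section 13 orders 5 mg of dexamethasone into each uterine artery (10 mg per patient), but Section 36 dispenses an 8 mg preparation, which matches neither figure

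*Combined protocol and SAP*

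**What the plan says.** The dose appears in two places in the current protocol text.

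- **Section 13, Procedure technique.** Before embolization, "5 mg of IV dexamethasone or placebo are injected via the microcatheter placed in the uterine artery". After embolization on that side, "The same procedure is then repeated on the contralateral uterine artery". The dose sentence is italicised, which Section 13 uses to mark additions to standard care, so it defines the study intervention.
- **Section 36, Drugs or Devices.** "8 mg dexamethasone intravenous preparation or placebo will be dispensed in identical vials or syringes with unique serial numbers". The record described there is limited to serial numbers: "A log of the serial numbers will be kept in the pharmacy".

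Two other places bear on the dose without settling it. The Study Design text in Section 13 says the product is "delivered to the Interventional Radiology Department in identical containers with specific serial numbers", with no number of containers per patient. Section 7 reports that the reference study used "a single intravenous dose of 10mg of dexamethasone", and says of the trial drug only: "This will also be administered as a single dose, eliminating the need for a steroid taper". The supplied text gives no other mg figure for this trial.

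**The concern.** Dexamethasone is the only planned difference between the arms, so its dose should have one value throughout the protocol. Here the section that directs the operator and the section that directs the pharmacy give figures that do not fit together.

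A pharmacy that supplies one Section 36 unit per patient cannot provide what Section 13 orders. The operator is blinded and receives a serial-numbered container. The supplied text gives no concentration, volume, split between arteries or discard rule with which to resolve the mismatch. Nor would the planned records reveal what was given: Section 36 describes a log of serial numbers, and the data list in Section 15 does not include the mg or volume injected.

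The stake is the meaning of the result. The trial could be reported as a test of 10 mg when 8 mg was given. The hypothesis in Section 7 rests mainly on a study that used 10 mg, and Section 9 attributes the larger expected effect to the intra-arterial route. If 8 mg was given, dose as well as route would differ from that study.

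**Working it through.** **Inputs**

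| Quantity | Value | Source |
|---|---|---|
| Dose injected per artery | 5 mg | Section 13, Procedure technique |
| Arteries injected | 2 | Section 13, Procedure technique |
| Preparation dispensed | 8 mg | Section 36 |
| Containers per patient | not stated | Sections 13 and 36 |
| Reference-study dose | 10 mg | Section 7 |

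**Step 1: can the 8 mg be derived from Section 13?**

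- One artery: 5 x 1 = 5 mg.
- Both arteries: 5 x 2 = 10 mg.

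Neither equals 8 mg. The 10 mg total equals the reference-study dose, which suggests it is the intent, although the protocol never states a total.

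**Step 2: can Section 13 be carried out with the Section 36 product?**

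| Reading of the 8 mg | Arithmetic | Delivered | Consequence |
|---|---|---|---|
| One unit per patient, split equally | 8 / 2 = 4 mg per artery | 4 + 4 = 8 mg | 10 - 8 = 2 mg short; 2/10 = 20% |
| One unit per patient, 5 mg used first | 8 - 5 = 3 mg for the second artery | 5 + 3 = 8 mg | 20% short in total; unequal sides |
| One unit per artery, 5 mg drawn from each | 8 - 5 = 3 mg left over; 3/8 = 37.5% | 5 + 5 = 10 mg | Fits Section 13, but needs a discard rule that is not given |
| One unit per artery, injected in full | 8 x 2 | 16 mg | Departs from Section 13 |

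The first three rows follow Section 13 as far as the supply allows and give 8 to 10 mg. The last row lies outside that condition. It is shown because the text tells the operator neither the concentration nor the volume that holds 5 mg.

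**Step 3: does this disturb the sample size?**

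Section 9 uses means of 2.89 and 3.91, SDs of 1.09 and 2, a 50% larger effect, two-sided 0.05 (Section 16 specifies two tails) and 21 per group.

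- Difference: 1.5 x (3.91 - 2.89) = 1.53.
- Pooled SD: sqrt((1.09^2 + 2^2) / 2) = 1.61.
- Power: 85.2% by the t test, 86.8% by the normal approximation.

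The stated 86% is reproduced. No mg dose enters the calculation, so the discrepancy leaves the figure unchanged.

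**The case against.** The strongest reply is that the sections describe different things: Section 13 states what is injected and Section 36 what is dispensed. A container may hold more than the dose, and Section 36 does not say one unit per patient. With one unit per artery and the excess discarded, exactly 5 + 5 = 10 mg is delivered. Section 13 is also the only place that gives a dose to administer, so it could be taken to govern. The pharmacist who compounds the product knows its content and might notice the mismatch. An appendix named in the contents list but not among the supplied text might hold the missing detail. Finally, if every treated patient receives the same amount, the comparison with saline remains valid, and the protocol describes dexamethasone as safe even at large doses.

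Some of this stands. A reconciling reading exists, the comparison between arms is not biased by a uniform dose error, and no safety harm is claimed. The statement that volume, split and discard instructions are absent applies to the supplied text only. However, the reconciling reading is stated nowhere in that text, and it needs 3 mg of each container to be left behind by an operator who is not told how to measure 5 mg. Even if an appendix gave the detail, two sections of the protocol would still carry figures that do not match.

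**Conclusion.** The protocol is wrong as written on the study dose. Section 13 implies 10 mg per patient and Section 36 supplies 8 mg in a unit of unspecified use; 8 mg equals neither the per-artery dose nor the total.

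The shortfall is 2 mg (20%) if 8 mg is the whole patient supply, and nil if 8 mg is per artery and 3 mg of each unit is discarded. The delivered total is therefore 8 to 10 mg, assuming that the operator follows Section 13 as far as the supply permits. That 10 mg is the intended total is an inference from 5 mg x 2 and from the reference-study dose. The point must be fixed because it concerns the definition of the intervention, even though randomisation, blinding and power are untouched.

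**What to change.** Make Sections 13 and 36 agree. Each should state the mg and volume per artery, the total mg per patient and the number of containers per patient. If the investigators and pharmacy confirm that 10 mg is the intent, one suitable wording is: two identical syringes per patient, each holding 5 mg of dexamethasone or the same volume of saline, one for each uterine artery, 10 mg in total. If 8 mg was intended, Section 13 should be changed to the matching per-artery dose.

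Add one item to the dispensing or procedure record for the mg and volume actually injected into each artery. Compile it so that blinded staff see only the volume. For any patient already treated, establish from pharmacy and procedure records what was given, and document it before the results are reported.

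The cost is small: a wording amendment to two sections and one added record item, with no change to sample size, randomisation or analysis.

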We intend to start the study by 10/2020 and to complete recruitment in 2 years, completing in 10/2022

Unless a patient chooses to opt-out of the study, a participant's duration will be limited to a total of 15 days beyond the procedural date. This will include periodic assessments of a subjective and objective measure, as outlined later in this proposal.

[figure not shown]
Enrollment and data analysis will be conducted on a rolling basis and deemed complete upon either meeting the primary endpoints (detailed below) or in the face of severe adverse events related to the procedural modification (detailed below).

12. Study Endpoints*

Primary end point of this study is post procedure pain. As such, pain is measured using a modified Visual Analogue Score (VAS), a numerical rating system that each patient assigns to their level of pain, at a particular time [28]. The study endpoints will include qualitative and quantitative collection of data. Pain following UFE is subjective and unique to each patient and can be based on the location, number of the fibroid(s) and the volume of fibroid(s). A modified VAS, termed *UFE Pain and PES Survey*, will be utilized to assess pain prior to and following the procedure (Pre, immediately after the procedure, and periodically for the next 13 days, as described below). Our primary endpoint will be a 3-point decrease in the UFE Pain & PES score between test and controls.

Secondary endpoints will include assessment of PES based on the measurement of nausea, vomiting, subjective fevers or chills, subjective data obtained from return to work times and readmission rates. This will be assessed in part using our *UFE Pain and PES Survey*, which includes a previously validated numerical scoring system

(0-3) to categorize nausea and vomiting, as well as a “Yes” or “No” scoring system to evaluate subjective fevers or chills.

13. Procedures Involved*

The Uterine Artery Embolization procedure with the proposed intervention is detailed below, italicized section denotes the interventions which are additions to the standard of care. The procedure is separated into Pre-Procedure Assessment and Imaging, Uterine Artery Embolization Procedure, and Post-Procedure Assessment and Imaging.

Pre-Procedure Assessment and Imaging:

- All accepted UFE study participants will be initially assessed using the attached UFE Pain & PES Survey to ascertain their current baseline pain.

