All patients will have a routine 2 week post-procedural phone call to review their symptoms, 1 month clinic visit and then 3 month clinic visit after MRI imaging.

All data collected from the Surveys will be stored and analyzed as described elsewhere in this proposal. Again, we expect that this study will reach its recruitment goal and Primary Endpoint in approximately 2 years.

To evaluate specific aim 1:

Pain will be assessed using 11 point visual analog scale as below:

The visual analog pain score will be documented as follows:

- Time 0 Immediately prior to the procedure
- 1 hour intervals for the first 3 hours
- 3 hour intervals for the next 9 hours
- 6 hour intervals for the next 12 hours
- Daily, for the next 3 days
- Once at day 7

First 3 of those surveys will be done in the recovery area. The amount of narcotic use from PCA pump will also be recorded.

To evaluate specific aim 2:

Post embolization syndrome will be assessed as reporting of nausea, vomiting and pain scores, that will be assessed at least twice during the day of the procedure and then daily for the next 3 days and then at 7 days. We will utilize our previously mentioned UFE Pain and PED Survey.

To evaluate specific aim 3:

Symptom relief, patient satisfaction and fibroid volume change will be measured through the completion of a UFE health-related quality of life (QOL) survey, UFE QOL Survey, prior to the procedure and then at 1 month and 3 month after procedure.

Uterine volume will be compared from the pre-procedure and 3 month post procedure MRI using volumetric software.

14. Data and Specimen Banking*

No specimen will be collected or stored. Data will be kept in password protected, HIPAA compliant University approved Box folder, accessible only to investigators.

15. Data Management*

All data will be stored, accessed, and analyzed utilizing server and computer workstations previously approved as HIPAA compliant. Data will be kept in password protected, HIPAA compliant University approved Box folder, accessible only to investigators. Anonymized data will include age, pre and post MRI imaging, UFE Pain & PES Survey, narcotic use, vital signs, subjective reports of nausea, vomiting, daily dietary intake, bowel movements, length of hospital stay, readmission rate, and days to return to baseline.

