A single computer system managed by the Pharmacology Research Coordinator, [name], will be maintained to ensure blinding of the cohorts. Collected data will be analyzed by [name], and done so prior to unblinding.

16. Provisions to Monitor the Data to Ensure the Safety of Subjects*

All data will be analyzed as it arrives and on a rolling basis by the primary physicians and researchers directly involved in this study, to ensure that the clinical findings and participant reported responses to the Pain & UFE Survey are not deviating in a way that could lead to undue harm.

As stated previously, all participants will be admitted to the hospital for observation for the first 24 hours and discharged with 2-week clinical follow-up in place and the contact information of a research team member. All participants will be contacted daily for the first 3 days, then at 7 and 14 days following the procedure. Any adverse effects of safety issues would be discovered in this follow up.

At 6 months we will analyze the interim data for any difference in the efficacy of treatment between the groups. All data will be analyzed using IBM SPSS software. We will use Student's T test for analysis of continuous variables, Chi square test for categorical variables with significance level set at two tailed p value of <0.05.

Although we expect that this trial exposes the participants to minimal risk, we consider the following statistically-significant differences between the two arms to be grounds for immediate trial termination: excessive abnormal uterine bleeding, infection, and sepsis.

17. Withdrawal of Subjects*

Subjects will be immediately withdrawn if it is deemed at any time prior to the procedure date that they fall into any of the previously outlined Exclusion criteria, suffer an intra-procedural adverse reaction to the use of dexamethasone, or willingly choose to leave the trial at any time.

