Once terminated from the trial, a subject can continue to undergo a UFE if they both meet the previously prescribed criteria and choose to do so. If a subject chooses to withdrawal post-UFE, a termination letter will be issued to their current address and all attained medical documents will be delivered through standard channels to their Primary Care Provider / referring physician. They can continue to receive standard post-UFE follow-up care through the University of Miami Interventional Radiology Department, if they so choose and without any punitive consequences. This is outlined in the Study Consent Form.

18. Risks to Subjects*

In this study, patients will be asked to assume the standard risks associated with UFE. These include known complications of bleeding, infection, adverse reaction to contrast agent, pain, need for further intervention/embolization. Further, there is a additional risk with the addition of a single dose of dexamethasone, as below which will be explained to patients.

Even at large doses, dexamethasone is known to have an excellent safety profile, with few adverse effects. Of those reported, anaphylaxis is exceedingly rare (incidence of ~ 0.1%) and the risk of transient hyperglycemia should be mitigated by the exclusion of pre-diabetic and diabetic patients (Determined by Hemoglobin A1c percentage) [29, 30]. It is important to note that there is no increased risk for delayed wound healing or infection in surgical patients receiving a single dose of dexamethasone [30]. Further, as a single dose will be administered, there is no need for a dedicated taper as suppression of the hypothalamic-pituitary-adrenal axis does not occur until weeks of steroid therapy.

19. Potential Benefits to Subjects*

If observed, the major benefit to women participating in the dexamethasone arm of this study will be a fall in pain level and PES following UFE. Other benefits may be a faster recovery and faster return to work or baseline activity.

20. Vulnerable Populations*

N/A

21. Multi-Site Research*

N/A

22. Community-Based Participatory Research*

N/A

23. Sharing of Results with Subjects*

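### Section 16 claims that contacts ending at day 14 will find every safety problem, yet no adverse-event collection is assigned to the 1- and 3-month visits already scheduled

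*Combined protocol and SAP*

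**What the plan says.** Section 16 of the combined protocol and SAP states that participants will be "contacted daily for the first 3 days, then at 7 and 14 days following the procedure". The next sentence is "Any adverse effects of safety issues would be discovered in this follow up". The same section makes a statistically significant difference between the arms in "excessive abnormal uterine bleeding, infection, and sepsis" grounds for ending the trial at once. It names the chi-square test for categorical variables at a two-tailed 0.05 level.

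Section 18 lists the standard UFE risks, including "pain, need for further intervention/embolization". Neither section says over what period these harms are counted.

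Section 11 says that a participant's "duration will be limited to a total of 15 days beyond the procedural date". Section 13 nevertheless plans a "1 month clinic visit and then 3 month clinic visit after MRI imaging", and adds: "Each patient will complete uterine fibroid symptom & health-related quality of life questionnaire prior to the procedure and then 1 month and 3 month after". The purposes given for this later follow-up are symptoms, quality of life, satisfaction and fibroid volume or treatment response.

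The data list in Section 15 includes the pain and PES survey, vital signs, length of stay and readmission. It does not name uterine bleeding, infection, sepsis or further intervention.

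**The concern.** The completeness sentence carries weight that nothing in the plan supports. If Section 16 is followed as written, active safety follow-up stops at two weeks, although the same women are seen twice more by the study team. A harm that arises in between is counted only if the patient volunteers it, if it leads to a readmission, or if someone notes it at a visit held for another purpose.

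Two things rest on that count. One is the between-arm comparison that can terminate the trial. The other is the final safety statement on a steroid delivered into the uterine arteries. Incomplete counting makes it easier to report no excess harm when there is one. It also leaves the reader unable to say what period a reported event rate covers.

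**Working it through.** **The plan's own figure.** The only computed figure is the 86% power for pain in Section 9. The difference is 1.5 × (3.91 − 2.89) = 1.53. The pooled SD is √((1.09² + 2²)/2) = 1.611, so the standardised difference is 0.95. With 21 per arm and two-sided α = 0.05, power is 86.8% by the normal approximation and 85.2% by the noncentral t. The figure reproduces. It concerns pain and says nothing about harms.

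**Coverage.** Scheduled safety contacts end at day 14, and the last planned visit is at about day 90. 14/90 = 16% of the follow-up already scheduled.

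**How few events decide the comparison.** For a 2×2 table with rows (a, b) and (c, d), the uncorrected statistic is χ² = N(ad − bc)² / [(a+b)(c+d)(a+c)(b+d)], with N = 42 and 21 per arm.

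- 4 vs 0: 42 × (4×21 − 17×0)² / (21×21×4×38) = 296,352 / 67,032 = 4.42, p = 0.036.
- 3 vs 0: 42 × (3×21 − 18×0)² / (21×21×3×39) = 166,698 / 51,597 = 3.23, p = 0.072.
- With one event in the other arm, the boundary lies between 6 vs 1 (p = 0.038) and 5 vs 1 (p = 0.078).
- Fisher's exact test needs 5 vs 0 (p = 0.048), since 4 vs 0 gives 0.107. The choice of test moves the boundary by an event but leaves the argument unchanged.

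**Effect of losing late events.** The documents give neither event rates nor times to onset, so both are assumptions here. Let p₁ and p₀ be true 3-month rates with dexamethasone and placebo. Let f be the fraction of events that occur by day 14, taken as equal in both arms, with nothing later captured (the worst case). Power is the sum of Bin(a; 21, f·p₁) × Bin(b; 21, f·p₀) over all a > b for which the uncorrected chi-square gives p < 0.05.

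| Assumed rates | f = 100% | f = 75% | f = 50% | f = 25% |
|---|---|---|---|---|
| 30% vs 5% | 61.7% | 45.9% | 25.5% | 5.3% |
| 30% vs 10% | 37.8% | 27.6% | 16.5% | 4.1% |
| 20% vs 5% | 31.1% | 20.6% | 9.4% | 1.5% |

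Under equal loss the rate ratio is unchanged (f·p₁ / f·p₀ = p₁/p₀), but the difference and the power shrink. The first column shows the other half of the picture: even complete capture gives modest power at this sample size.

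**The case against.** The strongest reply is that late harms are not ignored. Section 16 opens with rolling review of incoming data and sets no day-14 cut-off for it. Section 13 gives women self-monitoring instructions that include abnormal uterine bleeding, and an on-call number. Section 33 gives them an adverse-event form, and Section 25 has the team meet monthly and watch for adverse events. Readmission is an endpoint and a recorded item. The fibroid symptom questionnaire at 1 and 3 months may ask about bleeding; its content is not in the text available. The drug effects that Section 18 itself discusses, anaphylaxis and transient hyperglycemia, are acute. Finally, with 21 per arm, fuller capture would not make the safety comparison well powered.

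Much of this stands, and it limits the point. A reader might infer that the named harms mostly arise after day 14, or that further intervention cannot be seen or judged before the 3-month MRI. No section says so; the MRI's stated purpose is treatment response. A reader might also work out, from an assumed cycle length, how many women will have had no period by day 14. That is not the share of bleeding events missed, because the criterion is excessive abnormal uterine bleeding, which need not be menstrual. Nor do the documents support saying that later harms would be missed outright.

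What does not stand is the idea that these routes replace planned collection. Volunteered reports have no defined window and no denominator of women who were asked. Section 16 also draws its completeness claim from the scheduled contacts, not from these other routes.

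**Conclusion.** The point holds in this form: Section 16 asserts full detection by day 14 without justification, its termination harms and the re-intervention risk in Section 18 have no time window, and no section plans standard collection by arm at the 1- and 3-month visits. The two harm lists should be kept apart, since further intervention is a listed risk and not a termination criterion.

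The share of events affected cannot be computed from the documents. What can be said is that 3 vs 0 and 4 vs 0 fall on opposite sides of 0.05 for the uncorrected test, so one uncounted event can change the result. Under assumed 3-month rates of 30% vs 5%, power falls from about 62% to about 26% if half the events occur by day 14 and no later one is captured. Those rates and that fraction are illustrative, and power for moderate differences is low in any case.

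A reader might treat the 2-week contact, called clinical follow-up in Section 16 and a phone call in Section 13, as a contradiction. A call to review symptoms can serve as that follow-up, so this is not a substantive error. The 15-day participation limit in Section 11 does conflict with 3-month follow-up and needs reconciling. This is worth changing because the remedy is cheap, not because a large loss has been shown.

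**What to change.** - In Section 16, delete the completeness sentence, or soften it to say that the contacts to day 14 are intended to detect early adverse effects.
- Add that abnormal bleeding, infection, sepsis, readmission and further intervention are asked about with the same standard questions, and recorded with dates, at the existing 1- and 3-month visits as well as to day 14. Add to the Section 15 data list those items it does not yet name.
- State that these events are compared by randomised arm over 3 months.
- Reconcile the participation limit in Section 11 with the visits in Section 13.

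No visit is added, and 42 patients, the 86% power for pain and the treatment given are unchanged. The cost is slightly more recording at two visits and more background events to attribute, which blinded recording by arm can accommodate. The report should still say that a trial of 21 per arm has limited ability to detect differences in harm.
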